2.3 RISK/BENEFIT ASSESSMENT

2.3.1 Known Potential Risks

Efforts will be made to reduce physical and psychological stress associated with study participation. These procedures will be explained to the individual participants and to their parents/guardians.

- A. OrCam MyEye 2 Device and Use.** Non-significant risks are associated with the use of the device when following the manufacturer's User Guide (**Appendix J**). The device is worn as an accessory to regular eyeglass frames. The relative proportion of the device to a pediatric participant is shown in **Appendix K**. If an individual does not have glasses, they may experience discomfort with wearing glasses for the first time. The increase in auditory inputs may be irritating. The device use acclimation process may be frustrating. These are expected to improve with repeated use.
- B. Medical Evaluations.** Minimal risks are associated with the physical, the Unified Batten Disease Rating Scale (UBDRS), and neuropsychologic examinations. Multiple independent evaluations may be stressful to a child or an impaired participant.
- C. Ophthalmologic Evaluation.**
 A standard ophthalmologic exam includes dilation. Iris dilation can make participants transiently sensitive to light.
- D. Audiologic Evaluation.** For the hearing test the participant will wear headphones or soft foam earplugs. They will then be exposed to tones and words which vary in loudness and asked to respond to the sounds. This testing involves minimal discomfort.
 Acoustic reflex measurement allows the audiologist to further examine the integrity of the acoustic reflex arc which relies on functional integrity of the middle ear system, inner ear, seventh and eighth cranial nerves and auditory pathways in the lower brainstem. For this test, very brief, somewhat loud tones are presented to each ear. In a normal-hearing ear, the stapedius muscle in the middle ear contracts in response to loud sounds presented

at levels of about 70-100 dB HL (decibels hearing level). In this test, the audiologist presents tones at these levels and determines whether there is an acoustic reflex and what level of sound is required to produce the reflex. This is a standard audiology test.

The audiology evaluation will include measurement of auditory evoked potentials. For this test, the participants will wear either headphones or soft, foam earplugs. Electrodes will be taped to the participants' head and the electrical response to sound will be recorded. This testing involves minimal discomfort and risk.

- E. Neuropsychologic Evaluations.** Participants may fatigue or get frustrated from answering many questions. Breaks will be provided to minimize these potential issues.
- F. Phlebotomy.** An anesthetic cream such as EMLA may be used to decrease discomfort. Infection and bruising are possible at the site of the blood draw.
- G. Cheek swab/Saliva collection.** The collection may be inconvenient. The cheek swab may cause temporary oozing of blood that should be minimal.
- H. Urine collection.** This collection may be inconvenient.
- I. Skin biopsy.** The biopsy may hurt. This can be minimized by administration of local anesthetics. The site may leave a faint scar. Individuals with history of excessive keloid formation will not have a skin biopsy done. Bleeding and infection are minimal risks.
- J. Genetic Testing.** Genetic information obtained from participation in research could be misused for discriminatory purposes. However, state and federal laws provide some protections against genetic discrimination. Researchers who will have access to genetic information about the participants will take measures to maintain the confidentiality of this information. Individuals enrolled in this protocol would already have the diagnosis of CLN3-related conditions or a genetic cause of low vision, with its attendant risks of insurance and employment discrimination. If the underlying genetic cause for the low vision is not known and it is applicable to identify, then the participant will be referred to protocol "Evaluation of Patients with Genetic Disorders" (16-CH-0103). To the fullest extent possible, the investigators will not disclose to third parties any information about the participants without their expressed consent.
- K. Sample confidentiality.** Specimens not being used for clinical care or standard clinical tests which are sent to various laboratories will have identifiers removed and be coded. This code and clinical data will be maintained on password protected computers and in locked offices.
- L. Psychological Harms.** This protocol may reveal unexpected medical findings. If these medical findings can be evaluated and treated at the NIH-CC we will provide short term care for these findings. For any unanticipated medical findings that result in psychological stress, the medical team will provide counseling and support to the participant and the parents/guardians. If needed, the medical team can be reached by letter, phone, and email to address other uncertainties.
- M. Risk to Family Relationships.** This protocol is not likely to reveal unexpected family relationships such as adoption or misplaced paternity. If these issues do arise, we will not mention them to the participant or family members unless the issue is of clinical significance for the participant. Every attempt will be made to uphold the objective of privacy and participant autonomy.

2.3.2 Known Potential Benefits

This is a feasibility study of using the OrCam by children with CLN3 or low vision. No previous study of this device in this population has been done, thus information on known potential benefits are limited to the following:

- 1) The device provides an approach to augment visual inputs by translating these into auditory inputs, a sensory system apparently unaffected in children with CLN3 or low vision.
- 2) In adults with low vision, the device improves their ability to read text and recognize products[26]. It is advertised to improve the ability to recognize faces, colors, and report dates and times. These are functions integral in basic daily life tasks.
- 3) Appropriate use of the device may allow children with CLN3 or low vision to regain independence in some basic daily tasks and decrease care burden for family members.

2.3.3 Assessment of Potential Risks and Benefits

This protocol provides an intervention with the potential for benefits. The risk of the intervention, use of OrCam, is minimal. The research evaluations (Ophthalmology, Neuropsychologic, Audiology) are required to determine eligibility and carry minimal risks. The research evaluations (UBDRS, collection of biospecimens, genetic testing) add to the general understanding of the natural history of CLN3. For the non-CLN3 cohort the collection of biospecimens and genetic testing will serve as important pediatric control samples. These proposed procedures carry minimal risks.

3 OBJECTIVES AND ENDPOINTS

OBJECTIVES	ENDPOINTS	JUSTIFICATION FOR ENDPOINTS
Primary		
To assess: a) safety and b) feasibility of using OrCam MyEye 2 by children with CLN3 or low vision.	
a) Adverse events b) Feasibility test, Feasibility questionnaire, and Device use diary (see Section 9.4.2)
 
The assessment periods will be 1 week at study site and 1 month at home.
	
a) Collection of adverse event data is a standard method for evaluating safety in clinical trials. b) No validated, standardized tool is available to evaluate the feasibility of augmentative communication devices such as the OrCam. We modified the feasibility questionnaire used in an adult study [26] to provide appropriate adaptation for the pediatric cohort.

Secondary		
To assess the efficacy of using the OrCam by	1) Function Test – Efficacy Scores (see Section 9.4.3)	No validated, standardized tool is available to evaluate the efficacy of augmentative communication

OBJECTIVES	ENDPOINTS	JUSTIFICATION FOR ENDPOINTS
children with CLN3 or low vision.	2) Ability questionnaire (see Section 9.4.3) The assessment periods will be 1 week at study site and 1 month at home.	devices such as the OrCam. We developed a Function Test based on the device's advertised functions, our observations of the pediatric cohort in the Natural History study, and the one used in an adult study [26], to provide age and ability appropriate assessments.
Exploratory		
1) To compare the feasibility and efficacy of using the device between the CLN3 and non-CLN3 groups. 2) To optimize methods for assessing efficacy of visual accommodation/assistive devices for the CLN3/NCL population 3) To characterize parental objectives relating to vision-based functions for a child with CLN3 4) To assess unanticipated adaptive functions of using the OrCam. 5) To discover biochemical markers relevant to disease	1) Function test – Feasibility Scores, Feasibility, Ability, Applicability questionnaires 2) Function test – Feasibility Scores, Neuropsychologic evaluation (1-month), Feasibility, Ability, Applicability questionnaires 3) Ability, Applicability, Quality of Life questionnaires 4) Device use diary 5) Samples collection to complement Natural History	1) Individuals with CLN3 also have neurocognitive disability, whereas the non-CLN3 may not. These evaluations would provide perspectives on differences in the two groups. 2) Participants' and caregivers' perspective will be important towards informing future development of studies and interventions for visual function in the CLN3 cohort. 3) Collection of biospecimens will allow increase in numbers and statistical power for the biomarker discovery

4 STUDY DESIGN

4.1 OVERALL DESIGN

Individuals with CLN3 are anticipated to have vision loss and intellectual disability, but with preserved auditory function. We **hypothesize that an auditory-based assistive technology with a simple operating procedure, such as the OrCam, will be safe and feasible for use in a pediatric population, including those with CLN3, and will enhance their ability to obtain visually based information.** We propose a pilot study of 20 study participants to evaluate the safety, feasibility, and efficacy of using the OrCam in a cohort of the CLN3 pediatric population. Since no information is available on the safety, feasibility and efficacy of the OrCam in the

Abbreviated Title: Pediatric Optic-to-Audio Device Study

Version Date: March 8, 2022

pediatric population, we also propose enrolling 10 pediatric participants with low vision from non-CLN3-related causes. The primary and secondary objectives will be assessed using data from all 30 participants.

In this 2-cohort (CLN3 and non-CLN3), open-label, single-center study, we aim to determine:

- 1) the safety and feasibility
- 2) the potential clinical efficacy

of the use of OrCam in children, including individuals with CLN3.

4.2 SCIENTIFIC RATIONALE FOR STUDY DESIGN

Currently, there is no device similar to the OrCam available or in accepted use for individuals with CLN3. In addition, there is also no data available on the use of this device in children with low vision. Thus, a combined cohort of pediatric participants with and without CLN3-related disorders will optimize recruitment potential, and provide preliminary information for evaluation of feasibility and efficacy in pediatrics, and specifically in individuals with CLN3-related conditions. To assess efficacy, we will use the study participants' baseline data as controls. This option encompasses the least number of confounding factors for a cohort of small size.

In the CLN3 natural history study (18-CH-0002), accrual rate averages at 8-10 per year. Not all of these individuals will meet the eligibility criteria for this proposed study. However, we anticipate, based on experience with interventional trials of other rare diseases, that families hesitant to participate in an observational study would be more open to participating in an interventional study. Given these considerations, we anticipate an accrual rate of 5 participants per year and a reasonable potential to enroll 20 CLN3 participants over 2-3 years. We have also discussed potential eligible participants with local Ophthalmology groups (Howard University, Johns Hopkins, NEI), and the anticipated number for pediatric individuals with low vision and not CLN3-related condition is estimated to be in the same range. We plan to screen up to 50 participants.

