1 PROTOCOL SUMMARY

1.1 SYNOPSIS

Title:	Pilot Study of an Optic-to-Audio Device in a Pediatric Cohort with CLN3-related conditions or Low Vision
Study Description:	This is a pilot study of an augmentative visual device, OrCam MyEye 2 (OrCam), in pediatric individuals with CLN3-related conditions or low vision. We hypothesize that, given the relatively simple design and operating procedure of the device, the use of the OrCam by study participants will be safe and feasible. We also hypothesize that the device will enhance their ability to obtain visually based information.
Objectives:	
Primary Assess the safety and feasibility of OrCam use by children with CLN3 or low vision.
 
Secondary Assess the effectiveness of OrCam use by children with CLN3 or low vision.
 
Exploratory Assess the feasibility and effectiveness of OrCam use in CLN3 versus non-CLN3 groups. Optimize methods for assessing efficacy of visual accommodation/assistive devices for the CLN3/NCL population

Endpoints:	
Primary 1) Adverse events during the use of OrCam. 2) Feasibility test. 3) Feasibility questionnaire. 4) Device use diary. The assessment periods will be 1 week at study site and 1 month at home.
 
Secondary 1) Function test of using OrCam. 2) Ability questionnaire.
 
Exploratory 1) Function test. 2) Feasibility, Ability, Applicability questionnaires.

Study Population:	30 individuals age 6-18 years with low vision (20 with CLN3-related conditions, 10 without CLN3) of any gender, demographic, geographic location who meet study eligibility criteria.
Phase:	Not applicable
Description of Sites/Facilities	The NIH Clinical Center will be the only site enrolling participants.
Enrolling Participants:	
Description of Study Intervention:	The study uses the OrCam MyEye 2, a 22.5-g portable, eyeglass-mounted device that converts camera-captured inputs to auditory outputs. Its advertised functions include text reading, facial recognition, and product identification. The study participants and

Abbreviated Title: Pediatric Optic-to-Audio Device Study

[figure not shown]
Version Date: October 25, 2022

parents/guardians will be trained on how to use the device. Evaluations for primary and secondary endpoints will be done following 1 week and 1 month of device use.

Study Duration: 24-36 months.

Participant Duration: 1-2 months

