5.7 STRATEGIES FOR RECRUITMENT AND RETENTION

Participants will be recruited from the current 18-CH-0002 CLN3 Natural History protocol, through patient and professional organizations, at conferences, and through other healthcare providers. Study participants and parents/guardians may also contact the study team directly. We will also distribute information of this protocol through the NIH OPR, posting on clinicaltrials.gov, postings on social media websites, and referencing of this study website in presentations on CLN3-related topics. We plan to screen up to 50 participants for the duration of the study and enroll 5-10 per year for a total accrual goal of 30 participants.

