9.2 SAMPLE SIZE DETERMINATION

Since no prior research or data are available and these measures are developed specifically for this pediatric population with multiple disabilities, power calculation is not able to be determined. The study in 12 neurologically intact adults reported a mean improvement of 70% in performance over baseline on the Function Test. We anticipate that the improvement will be lower given the age and comorbidities in the CLN3 cohort, thus propose a total enrolment of 30 pediatric participants. As outlined in **Section 4.2 Scientific Rationale for Study Design**, we anticipate being able to recruit 5 CLN3 and 5 non-CLN3 participants with low vision in one year.

A major purpose of this trial is to obtain pilot data on feasibility and potential functional outcome measures that appears to improve with device use. The pilot data will inform power calculations for a subsequent trial focused on establishing device intervention efficacy.

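### At the stated 5 CLN3 participants per year, 10 to 15 are expected in 2-3 years, not 20, so the planned 20 + 10 cohort is not expected within 24-36 months

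*Combined protocol and SAP*

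**What the plan says.** The synopsis (Section 1.1) sets the population as "30 individuals age 6-18 years with low vision (20 with CLN3-related conditions, 10 without CLN3" and gives "Study Duration: 24-36 months", with "Participant Duration: 1-2 months".

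Section 4.2 starts from the natural history study: "In the CLN3 natural history study (18-CH-0002), accrual rate averages at 8-10 per year". It notes that some of those individuals will not be eligible here, and that an interventional study may attract other families. It then concludes "we anticipate an accrual rate of 5 participants per year and a reasonable potential to enroll 20 CLN3 participants over 2-3 years". For the other cohort it says "the anticipated number for pediatric individuals with low vision and not CLN3-related condition is estimated to be in the same range".

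Section 9.2 refers back to 4.2 and splits the rate by cohort: "we anticipate being able to recruit 5 CLN3 and 5 non-CLN3 participants with low vision in one year". Section 5.7 gives an overall rate: "enroll 5-10 per year for a total accrual goal of 30 participants".

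Section 4.1 says that the primary and secondary objectives use the data of all 30 participants. Section 9.4.7 applies the rules of 9.4.2 and 9.4.3 to the sub-groups.

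**The concern.** One sentence gives a rate, a target and a window, and the rate multiplied by the window does not give the target. The CLN3 cohort is two thirds of the planned sample, and it is the population named in the feasibility hypothesis of Section 9.1.

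Two things are at stake. If enrolment follows the stated rate and window and non-CLN3 stops at 10, the whole shortfall falls on the CLN3 cohort and its sub-group results lose precision. If the total is instead filled with extra non-CLN3 participants, the mix behind the pooled rules changes. Section 3 expects the two groups to differ, because CLN3 carries neurocognitive disability that the other group may not have.

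**Working it through.** **Inputs.** CLN3 rate 5 per year (4.2, confirmed by 9.2). Non-CLN3 rate 5 per year (9.2). Overall rate 5-10 per year (5.7). Target 20 CLN3 + 10 non-CLN3 (1.1). Duration 24-36 months and participant duration 1-2 months (1.1).

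**Step 1: try to reproduce the plan's 20.** Expected number = rate × years.
- 5 × 2 = 10
- 5 × 2.5 = 12.5
- 5 × 3 = 15

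No point in the 2-3 year window gives 20. Time to 20 is 20 / 5 = 4 years. The rate needed is 20 / 3 = 6.7 per year for 3 years, or 20 / 2 = 10 per year for 2 years. If 5 per year were the rate for all participants, the gap would be larger: 10-15 in total over 2-3 years.

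**Step 2: totals by cohort at 5 + 5 per year.**

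| Months | CLN3 | Non-CLN3 held at 10 | Total | Total with no cap |
|---|---|---|---|---|
| 24 | 10 | 10 | 20 | 10 + 10 = 20 |
| 36 | 15 | 10 | 25 | 15 + 15 = 30 |
| 48 | 20 | 10 | 30 | 20 + 20 = 40 |

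Under the planned composition, CLN3 is 10 short (50%) at 24 months and 5 short (25%) at 36 months.

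**Step 3: Section 5.7.** 30 / 10 = 3 years and 30 / 5 = 6 years. Only the top of the 5-10 range fits 36 months.

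**Step 4: follow-up of the last participant.** If 1-2 months of participation must also fit inside 36 months, enrolment lasts 34-35 months. CLN3 is then 5 × 34/12 = 14.2 to 5 × 35/12 = 14.6, and the uncapped total is 10 × 34/12 = 28.3 to 10 × 35/12 = 29.2.

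**Step 5: chance variation.** The documents give no accrual distribution. With Poisson accrual as an assumption, the probability of at least 20 CLN3 participants is 0.003 at 2 years (mean 10) and 0.12 at 3 years (mean 15).

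**Step 6: CLN3 sub-group precision.** Exact (Clopper-Pearson) 95% intervals for a pass rate near 50%:
- 10/20: 27% to 73%
- 8/15: 27% to 79%
- 5/10: 19% to 81%

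**Step 7: effect of the mix on a pooled rule.** The pooled pass rate is the CLN3 share times the CLN3 rate, plus the remaining share times the non-CLN3 rate. Going from 20 + 10 to 15 + 15 cuts the CLN3 share from 2/3 to 1/2, so the pooled rate moves by one sixth of the gap between the groups. Pass rates are not in the documents. As assumptions, a gap of 10 points moves the pooled rate by 10/6 = 1.7 points, and a gap of 35 points moves it by 35/6 = 5.8 points. With assumed pass rates of 35% (CLN3) and 70% (non-CLN3):
- 20 + 10: (7 + 7) / 30 = 46.7%, below the 50% feasibility threshold
- 15 + 15: (5.25 + 10.5) / 30 = 52.5%, above it

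**The case against.** **Thirty participants can be reached in time.** A reader might infer from the mismatch that a total of 30 is out of reach in 24-36 months. The documents do not support that. The 5 + 5 per year of Section 9.2, and the top of the range in 5.7, both give a headcount of 30 at 36 months. What is not expected is the planned 20 + 10.

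**These are projections.** Section 4.2 speaks of anticipation and potential, so the supportable wording is that 20 is not expected, not that it is impossible. Section 5.7 also recruits from current natural history participants, of whom Section 2.2 mentions 22 initially enrolled, so early accrual could be faster. This stands as a qualification. However, the documents give no rate for such a head start. The 5 per year is stated after eligibility and willingness to join have been weighed, so the 8-10 per year of the other study cannot replace it.

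**The decision rules do not need 30.** A reader might also infer that 30 is a fixed denominator for every rule. It is not. The rules in 9.4.2 and 9.4.3 are percentages or changes in a proportion, and they work with 25 participants. Section 9.3.2 also limits who is evaluable for response. A smaller cohort costs precision and leaves the rules intact.

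**The sample size does not rest on accrual alone.** Section 9.2 says that power cannot be determined and proposes 30 because less improvement is expected than in the adult study. Section 9.4.3 offers simulations at N = 10. This stands: a CLN3 cohort of 10-15 is no smaller than the N simulated there.

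**Slow accrual may simply lengthen the study.** No calendar date is among the termination circumstances in Section 10.2. That is a fair point about consequences, but the stated duration would then be wrong.

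None of this reconciles 5 per year with 20 in 2-3 years.

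**Conclusion.** The inconsistency is real and rests on the plan's own figures. The rate, the CLN3 target and the window in Section 4.2 cannot all hold as expectations. At 5 per year the expected CLN3 cohort is 10 at 24 months and 15 at 36 months, and 20 takes about 48 months. With non-CLN3 held at 10, the total at 36 months is about 25. Reaching 30 by then means 15 + 15, which is 5 more non-CLN3 participants than planned.

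These figures assume steady accrual at the stated average. The 12% chance of 20 CLN3 participants by year 3 adds a Poisson assumption, and the shift in a pooled rule depends on assumed pass rates.

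The consequence is limited to cohort size, composition and sub-group precision. The sample size is not power-based, the main analyses are pooled, and the design is not invalidated. The figures should still be corrected, because the trial relies on them and correction is cheap.

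**What to change.** Make Sections 1.1, 4.2, 5.7 and 9.2 consistent by one of the following:

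- **(a) Duration.** Keep 20 CLN3 at 5 per year and restate the study duration as about 48 months plus the last participant's 1-2 months.
- **(b) Cohort.** Keep 24-36 months and restate the expected CLN3 cohort as 10-15 (total 20-25 with non-CLN3 at 10). Give the wider CLN3 sub-group intervals from Step 6 alongside.
- **(c) Rate.** If 5 per year is the wrong figure, restate it and justify a CLN3 rate of at least 6.7 per year for 3 years (10 per year for 2 years), for example by saying how many current natural history participants are expected to be eligible and willing.

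Whichever is chosen, state whether non-CLN3 enrolment is capped at 10. If it is not, say how a mix other than 20 + 10 will be handled when the pooled rules are read, at the least by reporting each rule by cohort next to the pooled result.

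The cost is protocol wording, with either a longer stated duration, a smaller stated CLN3 cohort, or a short justification of a higher rate. No procedure or assessment changes.
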